patients must be in New York Heart Association (NYHA) class II, III, or IV with a left ventricular ejection fraction (LVEF) of ≤40%. The inclusion and exclusion criteria are shown in Table 1. A total of 165 patients will be included over 6 month. In total, 11 hospitals (local investigators) in Belgium with an HF clinic employing at least one certified HF nurse will be participating in patient recruitment. Patients are not randomised and will all be participating in the smartphone digital support intervention.

A screening register will be kept including reasons why eligible patients that do not participate are disregarding inclusion. Patients refusing participation will also be asked to complete a quality of life (QOL)-questionnaire at 6 months and 12 months which will be answered online. A total of 165 patients (who do not want to participate) will be asked to answer this questionnaire.

So the app will be made available to 165 patients for home monitoring and another group of 165 patients without an application will be asked to answer quality of life questionnaires.

Patients who agree to use the application can continue to use it after the study, if they wish.

Inclusion criteria	Exclusion criteria
Diagnosed with HF – NYHA class II-IV	Acute coronary syndrome
LVEF ≤40%.	High urgent listed for heart transplantation
Hospitalisation due to decompensated HF at the moment of inclusion or up to 1 week prior to inclusion (i.e. discharged ≤1 week prior to inclusion).	Planned revascularisation, TAVI, MitraClip and/or CRT implantation within 3 months after inclusion
Owning a smartphone and able to use an application	Known alcohol or drug abuse
Written informed consent obtained	Terminal renal insufficiency with haemodialysis or peritoneal dialysis
	Impairment or unwillingness to use the digital support equipment (e.g. dementia, impaired self-determination, lacking ability to communicate)
	Existence of any non-cardiac disease reducing life expectancy to less than 1 year
	Age <18 years
	Participation in other treatment studies or remote patient management programmes

Table 1 – Inclusion and exclusion criteria. NYHA: New York Heart Association. LVEF: left ventricular ejection fraction. CRT: cardiac resynchronisation therapy. TAVI: transcatheter aortic valve implantation.

Digital support platform

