At inclusion, an account on the smartphone application will be created for the patient and the application will be installed on the patient's smartphone. Instructions on how to use the application will be provided. Patients will be included for 6 months in which they will be asked to use the different modalities of the smartphone application. There will be low-threshold contact with a study nurse if the patient doesn't use or doesn't know how to use the application, as well as when predefined alarm limits are crossed. In case of patients that are

very motivated to participate in the intervention but do not own a smartphone, a smartphone can be provided by the study sponsor for the duration of the study. No costs will be charged to the patient, also in case of loss or damage

Personalised alarm limits that can be predefined include:

- Heart rate: an upper rate will be set to detect possible atrial fibrillation
- Weight gain: ideal weight and alarm weight can be set by the case nurse.
- Blood pressure: hypotension (under normal limits for the specific patient) and extreme hypertension.
- Not using the application, no measurement input by the patient for a predefined time.

After 6 months the inclusion will be ended. If the patient and the care providers deems it necessary for the continuity of care, they may continue using the application after the 6 months period of the study. A new informed consent document should be signed and the application, inside or outside the study, will remain the same. Only the data collected during the 6-month period of the study will be used for the initial data analysis. Further data analysis of the additional data after 6 months may take place in a second stage. 6 months after the end of the study, during a routine appointment (standard of care) of the patient with his cardiologist, he will be asked to answer questions about his well-being again.

Data collection during the trial

Data that will be collected by the smartphone application and the caregiver application for analysis purposes throughout the trial includes parameter measurement (blood pressure, heart rate, weight), medication adherence by using the medication module, and patient-reported outcome questionnaires. In the caregiver dashboard application information on time spent on the caregiver dashboard application and all input (time spent, change in therapy, contacts) by caregivers (nurses, cardiologists, others) will be collected.

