Cost reduction between the intervention group, the historical cohort, and the participation refusals will be calculated. Costs and outcomes (utilities) will be compared by calculation of the incremental cost-effectiveness ratio (ICER) (ICER = $(\text{cost}_{\text{intervention group}} - \text{cost}_{\text{historical cohort}}) / (\text{effectiveness}_{\text{intervention group}} - \text{effectiveness}_{\text{historical cohort}})$). The incremental cost represents the difference in total average cost per patient between the intervention group and the historical cohort or the participation refusals. Effectiveness will be calculated by comparing QOL in the intervention group versus the participation refusals.

Study endpoints

The endpoints that will be assessed are summarized in Table 3. As specified before, the objectives of the study are to demonstrate positive implementation measures (e.g. feasibility) as well as to demonstrate cost-effectiveness. Secondary objectives include assessment of clinical impact, based on measurement of clinical endpoints as specified in Table 3. Implementation outcome variables will be assessed using a mixed-method design. Patient and caregiver parameters will be calculated (e.g. time spent using the application). Questionnaires will be used to assess patient variables. Semi-structured interviews in a selection of patients and caregivers will be performed to assess further outcome variables regarding implementation.

Implementation outcome variables	
Feasibility and patient acceptability	SUTAQ, semi-structured interviews.
Caregiver acceptability and burden of care	SUTAQ, semi-structured interviews, daily time spent by case nurses using the platform
Adoption and sustainability	Number and percentage of patients refusing inclusion, of patients continuing application usage after 6 months. Total time-percentage ratio of patients using the application throughout the trial.
Implementation cost	Cost-related data: healthcare resource use, hospital days, tests, procedures, health expenditure. Cost-effectiveness: healthcare cost data, WPAI questionnaire, ICER. Cost of hospital stay at inclusion.
Quality of life, literacy and patient self-care	KCCQ-12, EQ5D, HeartQoL, PHQ9, HLS-EU-Q16, EHFSB-9, SUTAQ.
Clinical outcome measurement	
Combined endpoint	Unplanned CV readmission and all-cause mortality

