Individual endpoints	Symptom control (NYHA, KCCQ-12), emergency department visits, length of hospital stay during the trial, unplanned CV readmission, all-cause mortality.

Table 3 - Study endpoints. CV: cardiovascular. SUTAQ: Service User Technology Acceptability Questionnaire. KCCQ-12: Kansas City Cardiomyopathy Questionnaire. EQ5D: EuroQol 5-dimension questionnaire. HeartQoL: Health-related quality of life questionnaire. PHQ9: patient health questionnaire-9. HLS-EU-Q16: European Health Literacy Survey Questionnaire. EHFSB-9: European Heart Failure Self-care Behaviour scale revised into a nine-item scale. SUTAQ: Service User Technology Acceptability Questionnaire. WPAI : work productivity and impairment. ICER: incremental cost-effectiveness ratio.

Statistical analysis

Sample size

A total of 165 patients will be included in the study. The sample size is based on comparable implementation trials (9,10). An additional patient group will be included that is not part of the study intervention but will complete questionnaires; this is a non-randomized control group. A minimum of 165 patients will take part in this control group for completion of the study.

Statistical analysis

The primary analyses will be paired Student *t*-tests and Wilcoxon signed-rank tests comparing baseline, 6-month and 12-month values for all patient-level outcomes. Secondary analyses aimed at determining the longitudinal impact of the smartphone digital support programme (i.e., using outcome data from the additional time points), and the correlation of independent variables (e.g., patient characteristics and adherence rates) with outcomes will be analysed using general linear mixed-model procedures. In addition, descriptive statistics will be produced for all variables collected, and subgroup analyses will be performed. All statistical analyses will be performed using the statistical software application SPSS (IBM Corporation, USA).

Descriptive statistics will be produced for the indicators of the implementation outcome to provide an objective measure of implementation success.

Discussion

The Bedicare-HF study is the first study that will investigate implementation of a smartphone-based HF digital support system in a real-life context on the background of European GDPR and medical device regulations.

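### Burden of care is measured as nurses' daily platform time without the number of patients monitored, so it mixes work per patient with accrual and site recruitment

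*Protocol*

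**What the plan says.** In the protocol's Table 3 (Study endpoints), the row on caregiver acceptability and burden of care lists the SUTAQ, semi-structured interviews and "daily time spent by case nurses using the platform". The last is the only measure of workload in the row, and it is stated per day.

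The section on data collection during the trial says that the caregiver dashboard will supply "information on time spent on the caregiver dashboard application and all input (time spent, change in therapy, contacts) by caregivers". Neither place mentions active patients or patient-time.

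Three other statements fix how caseload will move:

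- Patient recruitment: "A total of 165 patients will be included over 6 month", and "In total, 11 hospitals (local investigators) in Belgium" take part.
- Smartphone intervention: "Patients will be included for 6 months in which they will be asked to use the different modalities of the smartphone application".
- Same section: patients and care providers may agree to go on, in that "they may continue using the application after the 6 months period of the study", while "Only the data collected during the 6-month period of the study will be used for the initial data analysis".

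The statistical analysis section plans only this for such indicators: "Descriptive statistics will be produced for the indicators of the implementation outcome to provide an objective measure of implementation success".

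**The concern.** With staggered entry, a centre's monitored caseload is small at first, peaks when recruitment closes, and declines as patients reach month 6. A nurse's minutes per day follow that curve. A descriptive summary of daily time therefore reflects three things at once: the work each patient generates, the shape of accrual, and how many patients the centre recruited. Only the first describes the intervention.

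Implementation measures are a main objective of this trial, with clinical impact secondary, and the discussion names reimbursement in Belgium as a consequence of a successful result. A hospital or payer planning a service wants the nurse time that a given number of monitored patients will require. Minutes per day from a trial that was filling up and then emptying do not answer that. A comparison of daily time between centres could largely reproduce their recruitment order.

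**Working it through.** The protocol states no workload or caseload figure, so there is none to reproduce. The check derives the caseload from the protocol's own design figures.

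**Inputs**

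- N = 165 patients, accrual A = 6 months, 11 centres (patient recruitment).
- Participation F = 6 months per patient (smartphone intervention).

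**Base case.** Assume that nurse time is proportional to active caseload, that it is averaged over all days from first entry to last exit, and that no use after month 6 is counted.

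- Total patient-months = N × F = 165 × 6 = 990.
- Time from first entry to last exit = A + F = 12 months.
- Mean caseload = 990 / 12 = 82.5.
- Peak caseload = 165, at month 6, when all have entered and none has finished.
- Ratio = 82.5 / 165 = 0.50.
- Per centre: 165 / 11 = 15 at peak, and 15 × 6 / 12 = 7.5 on average.

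The ratio does not depend on the entry pattern, because total patient-months and the 12-month span are fixed. A numerical check gave 0.50 for even, front-loaded and back-loaded entry. With even entry it also stayed at about 0.50 with 10% to 30% linear attrition, or with a first month two to three times heavier than later months.

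**Other assumptions** (none is given in the protocol)

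| Change to the base case | Mean / full caseload |
|---|---|
| Average over months 0–6 only, even entry | 0.50 |
| Same window, back-loaded or front-loaded entry | 0.33 or 0.67 |
| Average over months 3–9 | 0.70–0.75 |
| Share c continues to month 12, even entry: 0.50 + 0.25c | 0.50–0.75 |
| All continue, back-loaded or front-loaded entry | 0.67 or 0.83 |
| Fixed daily overhead f of 20% or 40% of full-load time: f + (1 − f) × 0.50 | 0.60 or 0.70 |
| Accrual takes 3, 9 or 12 months (mean / peak) | 0.67, 0.60 or 0.67 |

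Most of these lie between 0.5 and 0.75. The values outside that range are 0.33 and 0.83.

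**Between centres.** Take two centres with the same work m per patient-week and the same entry pattern, one with 15 patients and one with 5, each followed for 26 weeks.

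- Patient-weeks: 15 × 26 = 390 and 5 × 26 = 130.
- Logged time: 390m and 130m, so daily time at the smaller centre is 130/390 = one third.
- Time per patient-week: 390m/390 = m and 130m/130 = m.

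Daily time differs threefold and the rate not at all. If instead a fixed overhead of 20% to 40% of the larger centre's full-load time exists at both centres, daily time at peak at the smaller one is 0.2 + 0.8/3 = 0.47 or 0.4 + 0.6/3 = 0.60 of the larger one's. Its time per patient is then 1.4 or 1.8 times as high (0.47 × 3 and 0.60 × 3). The rate is therefore free of caseload only under proportionality, which is a reason to show caseload beside it.

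**The case against.** **The protocol names a variable, not a summary.** It does not say that minutes will be averaged from first entry to last exit, that days without patients count, or that centres will be ranked. A statistical analysis plan, not available here, could supply the window and a denominator. This stands against treating the factor of two as a result of the plan. It does not remove the point, because the endpoint table does fix the unit, time per day, and that unit carries no caseload.

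**Daily time is a legitimate burden measure.** A nurse following 5 patients does carry less load than one following 15, and SUTAQ and interviews sit in the same row. This stands, and is why daily time should be kept. It answers how loaded the nurse was, not how much work a monitored patient creates.

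**Cost.** A reader might infer that the intervention cost is understated in the same way. The documents do not support that. The health economic analysis counts personnel time for inclusion and for following up alarms, and expresses cost as an average per patient. Total time divided by patients does not depend on the accrual curve.

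**Data for a finer split.** A reader might also infer that time by month since inclusion can be had from existing logs. The protocol says that dashboard time is recorded, but not that it is recorded per patient, so inclusion dates alone may not give that split.

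**Consequence.** The basic rate can still be computed after the trial if time logs and dates are kept, and no test or threshold rests on it. That limits the weight of the point.

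**Conclusion.** The point holds as a weakness in how a named implementation outcome is defined. Daily platform time, unrelated to the number of patients monitored, mixes work per patient with accrual and recruitment. Under the base-case assumptions the trial average is about 50% of the full-caseload workload, and roughly 0.5 to 0.75 under most alternatives. Half is a base case and not a constant, since the protocol states neither proportionality nor an averaging window. The between-centre problem does not depend on the averaging window: centres with fewer patients appear less burdened for equal work per patient.

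The consequence is confined to interpreting and scaling this descriptive indicator. The sample size, the paired tests and the cost-effectiveness calculation are untouched. A correction is worth making because implementation is a main objective and reimbursement a stated use.

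**What to change.** In Table 3, keep daily time as the description of nurse load. Add, as the measure for comparing centres and scaling up, total logged nurse time divided by patient-weeks under monitoring. Count a patient-week while the patient is alive, not withdrawn and within the 6-month period. Report the rate by site, with the active caseload shown beside it.

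Two details should be settled in the same edit:

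- Numerator and denominator must cover the same patients. If dashboard time cannot be separated for patients who continue after month 6, say so and show how many there were.
- Separate onboarding from steady state only if the dashboard logs time per patient. The sponsor should confirm whether it does.

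No change to the cost analysis is needed on this ground. The basic rate uses the dashboard time logs with inclusion and exit dates, so the cost is a little extra analysis work.

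### The refuser control group has two incompatible size statements, its membership depends on an ambiguous exclusion for unwillingness, and the ICER formula takes effectiveness from a cohort with no planned quality-of-life data

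*Protocol*

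**What the plan says.** **Size of the group.** Patient recruitment plans the app arm as "A total of 165 patients will be included over 6 month". For those who decline it says "A total of 165 patients (who do not want to participate) will be asked to answer this questionnaire", and then, summarising, "another group of 165 patients without an application will be asked to answer quality of life questionnaires". The Sample size section sets a different kind of target: "A minimum of 165 patients will take part in this control group for completion of the study". Health economic analysis speaks of collecting quality of life (QOL) and costs in a selection of refusers, with no selection rule.

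**Who counts as a refuser.** Patient recruitment has the app offered to every eligible patient in a consecutive series, and adds: "A screening register will be kept including reasons why eligible patients that do not participate are disregarding inclusion". Table 1 lists as an exclusion "Impairment or unwillingness to use the digital support equipment", followed by examples such as dementia and inability to communicate. Table 1 also requires "Owning a smartphone and able to use an application", while Smartphone intervention says that for patients who are "very motivated to participate in the intervention but do not own a smartphone, a smartphone can be provided by the study sponsor".

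**What the group is for.** Table 3 lists the percentage declining inclusion as an adoption outcome. The text of Health economic analysis takes effectiveness from QOL in app users against refusers. The ICER formula in the same section subtracts effectiveness in the historical cohort. For that cohort the section lists only hospital bills and administrative data.

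**The concern.** A number of people asked and a minimum number taking part are different quantities, and the second is tied to completion of the study. A site or sponsor reading the protocol cannot tell whether 165 approaches are enough or whether 165 respondents must be reached.

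Membership of the group is also open to two readings. The register covers eligible non-participants. If unwillingness to use the equipment makes a patient ineligible, someone who declines because of the app can be logged as excluded at one hospital and as a refuser at another. For a study of app adoption, these are the refusals of most interest. The smartphone criterion raises the same question about the denominator: it is unclear whether a patient without a phone is ineligible or can be offered the study.

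At stake are the refusal percentage and the only comparator with planned QOL data. The ICER formula adds a third problem, because as printed it needs an effectiveness value that the protocol does not plan to collect.

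**Working it through.** **Inputs.** From the protocol: 165 app users and 165 refusers (asked, or as a minimum taking part). The protocol gives no refusal rate *r* and no response rate *p*; the values below are assumptions. There is no stated calculation to reproduce, because the 165 rests on comparable trials.

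**Step 1: asked versus taking part.** Respondents if 165 are asked = 165 × *p*.
- *p* = 100%: 165
- *p* = 80%: 165 × 0.8 = 132
- *p* = 60%: 165 × 0.6 = 99

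Conversely, 165 respondents need 165/*p* refusers asked: 165/0.8 = 206.25, so 207; 165/0.6 = 275.

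**Step 2: what the minimum implies about refusal.** Suppose refusers come from the same offers that produce 165 app users. Then 165/*p* refusers are needed beside 165 acceptors, so the required refusal share is (165/*p*)/(165/*p* + 165) = 1/(1 + *p*).

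| Response *p* | Refusal needed | Offers, 165 + 165/*p* |
|---|---|---|
| 100% | 1/2 = 50.0% | 330 |
| 80% | 1/1.8 = 55.6% | about 371 |
| 60% | 1/1.6 = 62.5% | 440 |

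In the other direction, when the 165th patient accepts, the expected number of refusers is 165*r*/(1 − *r*). At *r* = 30% this is 165 × 0.3/0.7 ≈ 71 (about 57 respondents at *p* = 80%). At *r* = 40% it is 165 × 0.4/0.6 = 110 (88 respondents).

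**Step 3: effect on precision.** The 95% half-width for a difference in means, in SD units, is 1.96 × √(1/165 + 1/*n*), taking all 165 app users as observed.
- *n* = 165: 0.22
- *n* = 99: 0.25
- *n* = 71: 0.28
- *n* = 57: 0.30

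**Step 4: direction of the exclusion effect.** Let *R* be the true number of refusers beside 165 acceptors, and *f* the fraction logged as excluded for unwillingness. The reported refusal share is *R*(1 − *f*)/[165 + *R*(1 − *f*)], which falls as *f* rises. With *R* = 165 it runs from 165/330 = 50% at *f* = 0 to 0% at *f* = 1. These are the bounds for that *R*, not an estimate; nothing in the protocol informs *f*.

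**Step 5: the ICER, side by side.** The formula's denominator is effectiveness in app users minus effectiveness in the historical cohort. The sentence on effectiveness names refusers instead. The sentence on incremental cost allows either group. The data listed for the historical cohort contain no QOL, so the formula's denominator cannot be computed on the QOL measure that the text specifies.

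**The case against.** Several points on the other side stand.

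- **Only two size statements conflict.** A reader might infer a third size from the reference to selected refusers. It gives no number, and drawing 165 from all refusers would itself be a selection. It leaves the selection rule open but does not add a conflicting figure.
- **Taking part could mean entering the group and then being asked.** On that reading, only a fixed total against a minimum remains. The wording about completion of the study makes this reading less natural, and the text does not settle it.
- **The exclusion does not remove refusers as a class.** A reader might infer that Table 1 empties the comparator. It reaches only those unwilling to use the equipment; people who decline for other reasons stay eligible. Its examples describe incapacity, Patient recruitment and Table 3 treat refusers as people to be counted, and the Discussion expects information on them. The fault is ambiguous wording, not a demonstrated bias.
- **An overrun of app enrolment is not shown.** A reader might infer that the study would have to enrol well beyond 165 app users, or run well past 6 months, to find enough refusers. The 6 months describe the app arm. The control window is unstated, nothing says that app enrolment stays open, and refusal above 50% is not shown to be implausible.
- **Headcount is not the main limit on this comparison.** Refusers select themselves, and Patient recruitment schedules their QOL at 6 and 12 months only, with no baseline form mentioned. Those features weigh more than 165 against 99 respondents.

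None of this reconciles the two size statements, the formula with its text, or Table 1 with the smartphone provision.

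**Conclusion.** The point holds as an inconsistency to be corrected, of moderate weight. The statements on the number asked and the minimum taking part agree only at 100% response. If both groups come from one series of offers, the minimum also presupposes at least 50% refusal, a condition that the protocol neither states nor supports. The shortfalls of 132 and 99 rest on assumed response rates. The loss of precision is limited, from 0.22 to 0.30 SD in the least favourable case shown.

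The unwillingness wording, followed literally, can only lower the refusal percentage and thin the QOL comparator; its size cannot be estimated. The ICER formula contradicts its own text and rests on a cohort without planned QOL data. The two smartphone provisions contradict each other. The paired baseline-to-follow-up analyses named as primary do not use the refuser group and are not affected.

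**What to change.** 1. **Table 1, exclusion.** Delete the words on unwillingness so that the criterion covers incapacity only. Log unwilling but otherwise eligible patients as refusers in the existing screening register, and compute the refusal percentage over all offers to otherwise eligible patients. Written consent remains an inclusion criterion, so nobody is enrolled against their wishes.
2. **Size of the group.** Replace the minimum in Sample size with one statement used there, in Patient recruitment and in Health economic analysis: how many refusers are approached, how they are chosen, over what window, and how many are expected to respond under labelled assumptions. This needs no additional enrolment and no wider cost collection.
3. **ICER.** Change the effectiveness term to the refuser group, with the cost difference taken against the same group, as the section already allows. Alternatively, state that no utility-based ICER is computed against the historical cohort.
4. **Smartphone.** Reconcile Table 1 with Smartphone intervention without widening eligibility, so that it is clear whether patients without a phone count in the refusal denominator.

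The cost is rewording and approval by the participating hospitals' Ethics Committees, which the protocol requires for any change to the study plan. The sponsor may have to accept a less favourable refusal figure and a smaller stated control group.

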Table 2 – intervention design. ECG: electrocardiogram. ePRO: electronic patient-reported outcome. NT-proBNP: N-terminal prohormone of brain natriuretic peptide. KCCQ-12: Kansas City Cardiomyopathy Questionnaire. EQ5D: EuroQol 5-dimension questionnaire. HeartQoL: Health-related quality of life questionnaire. PHQ9: patient health questionnaire-9. HLS-EU-Q16: European Health Literacy Survey Questionnaire. EHFSB-9: European Heart Failure Self-care Behaviour scale revised into a nine-item scale. SUTAQ: Service User Technology Acceptability Questionnaire. WPAI : work productivity and impairment.

Health economic analysis

The costs considered for the cost-effectiveness analysis are direct costs of the smartphone-based digital support intervention and the care utilisation recorded during the inclusion of the trial. The costs for the digital support intervention consist of costs for data management using the application, costs for devices that are provided in selected patients (blood pressure monitor, weighing scale), and personnel costs for inclusion and time spent on follow-up of alarms.

Information on care utilisation will be collected at the end of the trial. Former studies have demonstrated that hospitalisation costs are the key driver of HF-related costs (7,8). This study will thus focus on reduction in length of hospital stay and reduction in rehospitalisations after initial hospitalisation. The 30-day and 90-day rehospitalisation rates will be assessed. All hospital-related costs will be collected from the hospital billing and financial departments. A distinction will be made between scheduled and non-scheduled hospitalisations. Scheduled hospitalisations for elective procedures and scheduled visits with the cardiologist or general practitioner will not be included in the cost-evaluation.

Implementation cost and cost-effectiveness will be assessed in this trial following a pre-post economic model. A historical cohort of all patients hospitalised for HF on a cardiology ward in 2019 in all participating centres will be assessed for comparison. Hospital bills and hospital administrative data based on the international classification of disease (ICD)-codes will be collected. Propensity matching will be applied.

QOL and healthcare-related costs will be collected in selected patients refusing to participate in the smartphone intervention.

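### For quality of life and NYHA class the primary paired tests cannot separate recovery from an app effect; the only non-user contrast for quality of life has no starting score, and the ICER names two different effectiveness comparators

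*Protocol*

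**What the plan says.** **Timing and allocation.** Patients enter during a hospital stay for decompensated heart failure or up to one week after it (Protocol, Patient recruitment and Table 1). There is no randomisation and all enrolled patients use the app. NYHA class and the QOL instruments are recorded at baseline and month 6 (Table 2), and outcomes are re-evaluated at month 12.

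**Primary analysis.** The Statistical analysis section plans paired t-tests and "Wilcoxon signed-rank tests comparing baseline, 6-month and 12-month values for all patient-level outcomes". Mixed models are secondary, and no comparator is described for them.

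**Refusers.** Under Patient recruitment, patients who decline are "asked to complete a quality of life (QOL)-questionnaire at 6 months and 12 months"; the questionnaire is not named. Health economic analysis adds: "QOL and healthcare-related costs will be collected in selected patients refusing to participate in the smartphone intervention".

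**ICER.** The formula in Health economic analysis subtracts cost and effectiveness in the historical cohort. The cost difference is then said to be "between the intervention group and the historical cohort or the participation refusals". The section ends: "Effectiveness will be calculated by comparing QOL in the intervention group versus the participation refusals". For the 2019 cohort it says: "Hospital bills and hospital administrative data based on the international classification of disease (ICD)-codes will be collected".

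**Claims.** Objectives includes demonstrating effectiveness and cost-effectiveness. Study endpoints is milder: "Secondary objectives include assessment of clinical impact, based on measurement of clinical endpoints as specified in Table 3". The Conclusion again expects the results to show whether and how the system improves health outcomes.

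**The concern.** A patient scored during or just after a decompensation admission can be expected to feel better months later with or without an app, through recovery, regression to the mean and usual care. A test against that starting point with no comparator credits all of this to the period of app use. The month 6 versus month 12 pair avoids the acute baseline, but it too has no comparator.

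The refuser contrast could in principle help. But people who accept a digital programme may differ at the outset from people who decline it, and no starting QOL is taken from those who decline. The contrast matters because it supplies the effectiveness term of the ICER, and the Discussion links a successful result to reimbursement. If the ICER formula is followed literally, it calls for an effectiveness value from a cohort for which no QOL or utility source is described.

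**Working it through.** The protocol bases its 165 on comparable trials and gives no effect size, SD or power, so there is no stated figure to reproduce. The structural points come from the text. The arithmetic only shows size, and its recovery, gap and correlation values are assumptions.

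**1. Which source can supply which term**

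| Source | QOL at start | QOL at months 6 and 12 | Costs |
|---|---|---|---|
| Participants | yes | yes | yes |
| Refusers | none scheduled | yes, instrument not named | yes, in selected refusers |
| 2019 cohort | none described | none described | bills and administrative data |

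The refuser row is the only non-user row with QOL, and it has no starting value. The ICER formula takes its effectiveness comparator from the third row; the section's last sentence takes it from the second.

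**2. Paired test with no app effect.** Inputs: n = 165 pairs (protocol); two-sided 5% and a recovery of d SDs of the change score (assumed). The test statistic is noncentral t with 164 degrees of freedom and noncentrality d × √165; the critical value is 1.975.

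| d | Noncentrality | Probability of significance | Same with 132 pairs (20% loss, assumed) |
|---|---|---|---|
| 0.1 | 1.285 | 25% | 21% |
| 0.2 | 2.569 | 72% | 63% |
| 0.3 | 3.854 | 97% | 93% |

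**3. Bias in the refuser contrast with no app effect.** Let g be the starting gap in SDs and r the correlation between starting and follow-up QOL. In case 1 the gap acts only through the starting score, so the follow-up difference is g × r. In case 2 the gap is stable, so the follow-up difference is g. Adjusting for the starting score subtracts g × r; a change score subtracts g.

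| g, r | Case 1: unadjusted | Case 1: adjusted | Case 1: change score | Case 2: unadjusted | Case 2: adjusted | Case 2: change score |
|---|---|---|---|---|---|---|
| 0.2, 0.5 | 0.10 | 0 | −0.10 | 0.20 | 0.10 | 0 |
| 0.3, 0.6 | 0.18 | 0 | −0.12 | 0.30 | 0.12 | 0 |
| 0.4, 0.7 | 0.28 | 0 | −0.12 | 0.40 | 0.12 | 0 |

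For example, in the last row 0.4 × 0.7 = 0.28 and 0.28 − 0.4 = −0.12 (case 1), and 0.4 − 0.28 = 0.12 (case 2). The two unadjusted columns are what the plan as written puts into the ICER denominator. I give bias and not false-positive rates because the protocol names no test for this contrast and uses it as an ICER term. A starting score shrinks the bias in both cases, but neither method removes it in both.

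**The case against.** The strongest reply is that this is a declared implementation trial. The protocol says patients are not randomised, calls the refusers a non-randomised control group, and lists the lack of a distinct comparator as a limitation in the Discussion. The Statistical analysis section says only that values are compared; it never says the paired tests prove an app effect. Table 3 also places QOL among the implementation outcomes, for which descriptive statistics are planned, and the secondary mixed models relate patient characteristics and adherence to outcomes.

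Much of that stands. The paired tests are legitimate descriptions of change, and the fault lies in the causal wording of the Objectives and the Conclusion. But the admitted limitation points to the historical cohort, which carries no QOL, and it mentions neither the acute baseline nor the missing refuser baseline. The paired tests cover all patient-level outcomes, so QOL falls under them whatever its place in Table 3. The mixed models are not described as including non-users.

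Two stronger readings are tempting and not supported. A reader might infer that no analysis plan could adjust the refuser contrast at all. Only adjustment for starting QOL is ruled out; other characteristics could be used if they are recorded for refusers, for instance in the screening register. A reader might also infer that a starting gap would make up the whole ICER denominator. It enters only as far as it persists, and later divergence or selective response would contribute too, which a starting questionnaire would not cure.

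**Conclusion.** The point holds and should be fixed. Three things rest on the text alone: the paired tests cannot separate recovery from an app effect on QOL or NYHA class; the refuser contrast cannot be adjusted for starting QOL; and the ICER formula conflicts with the sentence that defines effectiveness, naming a cohort for which no QOL is described.

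The size depends on the assumptions shown. With no app effect, a recovery of 0.1 to 0.3 SD of the change score gives a significant paired test in 25% to 97% of trials. A starting gap of 0.2 to 0.4 SD biases the ICER denominator by 0.10 to 0.28 SD (correlation 0.5 to 0.7) or by 0.2 to 0.4 SD, depending on how it persists. The documents give no value for recovery, gap or correlation, and do not show which group would start better.

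The effectiveness objective and the effectiveness term of the ICER are affected. Acceptability, usage and refusal-rate outcomes are not, and the comparison of costs and rehospitalisation with the 2019 cohort does not turn on this point.

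**What to change.** 1. **Patient recruitment:** ask refusers to complete EQ5D and KCCQ-12 once, at refusal, and name the same two instruments for months 6 and 12.
2. **Health economic analysis:** make the participant-refuser QOL contrast, adjusted for starting score and centre, the main estimate, with change from baseline as a sensitivity analysis. Report both estimates with confidence intervals, and state that confounding by willingness to participate remains. Do not add a rule that withholds a conclusion when the two disagree. They rest on different assumptions and differ whenever there is a starting gap; in simulations of the six scenarios above with a true effect of 0.2 SD, only one of the two was significant in about 32% to 55% of trials.
3. **Statistical analysis, Objectives and Conclusion:** say that the paired tests describe within-group change, and limit the effectiveness wording to match.
4. **ICER:** reconcile the formula with the section's last sentence by using refusers for the QOL or utility term, and state which comparator supplies the cost term.

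**Cost:** one short form for at least 165 refusers, some of whom will not answer, so the adjusted contrast rests on those who do; an amendment approved by the ethics committees; and weaker effectiveness claims. If recruitment is over, only items 3 and 4 and the reporting part of item 2 remain possible.
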